3.0 Study Design

Twenty patients will be collected from this M.D. Anderson based study and the data will be combined with an identical 20 patient study that [name] started while at the Arizona Cancer Center. The Arizona study has enrolled 15 of the planned 20 patients (as of August 2008), and by combining these two studies we will have a total of 40 patients for final analysis.

Study Schema

Patients must have radiographic evidence of brain metastases, proven with CT or MRI so that we can stratify patients by the number of brain metastases. Additionally, they must have no prior history of cranial radiation (other than stereotactic radiosurgery). Once enrolled, patients will receive Tarceva (150mg PO QD) for at least 6 days prior to starting and during whole brain radiotherapy (WBRT). External beam radiation will consist of opposed laterals to a total dose of 3500cGy in 14 daily fractions.

Upon completion of external whole brain radiation, patients will continue taking Tarceva (150mg PO QD) until documentation of disease progression (unless treating physician feels that stopping Tarceva would adversely affect the patient) or if patients are unable to tolerate study drug due to toxicities. Patients will be allowed to stop taking Tarceva at any time during this trial. Following completion of WBRT patients will have a repeat MRI or CT at 1 month after completion of WBRT, and then at 3 month intervals, or sooner if indicated by symptom progression. Additionally, during active treatment period of this trial, patients will not be allowed to have surgical debulking of CNS tumors, or stereotactic radiosurgery of CNS lesions, as this need would correlate with progression of disease. Patients will be allowed to receive palliative radiation if needed to address symptoms. Patients will be allowed to dose reduce down to 50mg per day, and may also take a treatment break of up to seven days.

Survival will be compared to a database of patients with similar histologies and stratified according to their Recursive Partitioning Analysis (RPA) class and the number of brain metastases, at time of diagnosis (16). The RPA is a predictive tool used to estimate survival based on age, performance status, and presence of extracranial metastasis.

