5.6 Administration

Patients will receive only a 30-day supply of drug at a time, from the Investigational Pharmacy. The patient will be seen by the nurse once approximately every 30 days (+/- 7 days) to review number of pills taken during the previous 30 days (+/- 7 days), and to receive another 30 days of medication. If patients are unable to return for their follow up visits, we will review their mediations and current drug logs over the phone and their Tarceva refills will be mailed to them via the investigational pharmacy.

Patients will begin taking Tarceva at least 6 days before their first dose of radiation, daily during radiation therapy, and then daily until progression is documented (unless treating physician feels that stopping Tarceva would adversely affect the patient), adverse events warrant discontinuation or the patient decides to stop taking the medication.

Tarceva tablets should be taken once daily. Each Tarceva dose is to be taken with up to 200 mL (~ 1 cup or 8 oz) of water, and should be taken 1 hour before or 2 hours after meals or medications, including grapefruit juice, vitamins, and iron supplements.

For patients residing outside the U.S: Patients will receive a 90 day supply of Tarceva at a time, from the Investigational Pharmacy; The study PI will have physician-to-physician communication regarding protocol enrollment; a letter (Appendix G) will be sent to the home physician outlining the subject's participation and requesting the home physician agreement to supervise the subjects care. The home physician will be requested to provide any patient medication diaries, progress notes, hospitalization records, toxicities, tests, and procedures to the study PI or his research staff at MD Anderson within 48 hours. The home physician will be asked that any questions related to the study drug dosing, schedule, or side effects be directed to study PI. All life

threatening clinical events must be reported by the home physician to the study PI within 24 hours of documented occurrence. The home physician will be provided with study contact numbers for business and non-business hours.

Protocol required evaluations outside MDACC will be documented by telephone, fax or e-mail. Fax and/or e-mail will be dated and signed by the MDACC physician, indicating that they have reviewed it.

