6.2 Study Discontinuation

Once enrolled in this study, patients will be allowed to discontinue Tarceva at anytime during this study, before, during or after radiation and be considered "off active treatment". If for any reason a patient wishes to discontinue taking Tarceva they will be allowed to do so. Patients will also be allowed to stop radiation at anytime as well; however, doing so will preclude them from continuing to receive Tarceva. Patients will be allowed to have a drug break of up to seven days; however, longer breaks may lead to removal from the study based on the discretion of principal investigator. Additionally the principle investigator may choose to discontinue a patient at any time. All reasons for discontinuation of treatment must be documented. Patients will be considered "on active treatment" while they are taking Tarceva. Once Tarceva is stopped patients will be defined as "off active treatment" and will still undergo routine follow up and screening as per the study calendar (see section 6.0). If after disease progression the patient's treating physician feels it is in the best interest of the patient to continue Tarceva, they may do so and the patient may also receive other therapies while continuing the study drug Tarceva without having the patient terminated from the study. Monitoring and follow up will continue as per the study calendar (see section 6.0).

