7.0 Radiation Therapy

Radiation therapy will be given once per day, five days a week for 14 days. Radiation will be given at a dose of 250 cGy per day for 14 fractions for a total dose of 3500 cGy. Radiation will be delivered with 6MV photons using opposed lateral beams dosed to mid plane.

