11.2 Background

The primary objective of this study is to estimate the median survival of patients with brain metastases from non-small cell lung cancer treated with Tarceva combined with whole brain radiation therapy.

Gaspar et al. provides a definition of average survival for patients with brain metastases stratified into three classes based on age, KPS and control of primary disease. This information came from an analysis of 1200 patients from three earlier RTOG trials. Based on this study one can expect the following survival. (9)

Class 1 patients with KPS >70 and age <65yrs to live approximately 7.1 months
Class 2 patients not meeting Class 1 or 3 criteria, have an average survival of 4.2 months
Class 3 patients with KPS < 70 have an average survival of 2.3 months

This study will be conducted in parallel with an identical study at the University of Arizona that was started on March of 2006. So far this study has accrued 15 of 20 patients, as of 8/2008. From these initial 15 patients the vast majority fall into RPA class II, with the reaming falling into class I and a small percentage in class III. From the first 15 patients enrolled the 4 remain alive, of the patient that have passed away the median survival has been 9.5 months, while the RPA predicted survival was 4.2 months.

The data from the Arizona study will be combined with this study (based at MD Anderson) which will accrue an additional 20 patients, producing a total of 40 patients for analysis. Patients will be analyzed based on the intent-to-treat principle. We will also analyze the subset of evaluable patients. Evaluable patients are defined as those patients that have completed WBRT and Tarceva.

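### The evaluable subset in section 11.2 is selected on completing treatment, so its survival is likely to run high if counted from the first dose; the intent-to-treat result is not affected

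*Combined protocol and SAP*

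**What the plan says.** Section 11.2 sets the main rule: "Patients will be analyzed based on the intent-to-treat principle". It then adds: "We will also analyze the subset of evaluable patients". The definition follows: "Evaluable patients are defined as those patients that have completed WBRT and Tarceva". No time origin, landmark, test or supportive label is attached to this subset, and section 11.5.1.1, which sets out the survival analysis, does not mention it.

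Three other parts of the plan decide who can meet the definition.

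- **Timing.** Section 5.6: "Patients will begin taking Tarceva at least 6 days before their first dose of radiation". Section 7.0: "Radiation therapy will be given once per day, five days a week for 14 days", and "Radiation will be given at a dose of 250 cGy per day for 14 fractions".
- **Length of drug treatment.** Section 3.0: after WBRT, "patients will continue taking Tarceva (150mg PO QD) until documentation of disease progression". Sections 3.0 and 5.6 also let the drug end for toxicity or by patient choice, and section 6.2 lets it go on after progression if the treating physician wishes.
- **Stopping.** Section 6.2: "patients will be allowed to discontinue Tarceva at anytime during this study, before, during or after radiation". The same section lets patients stop radiation at any time, but those who do may not go on receiving Tarceva.

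**The concern.** Both conditions are met or failed after enrolment, and both are tied to how the patient fares.

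A patient who dies before the last fraction cannot have completed WBRT. The days needed to finish it are therefore survival time that every member of the subset is certain to have. A patient who stops radiation because of deterioration must also stop Tarceva, and so fails on both counts.

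The Tarceva condition cannot be applied as written. A drug taken until progression, intolerance or choice has no point at which a course is complete. It could mean the concurrent phase only, drug taken to progression, or simply no longer on drug. Two analysts could build different subsets from the same data.

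At stake is a second survival estimate that could look better than the intent-to-treat one even if the regimen did nothing. Section 11.0 says that a successful result would be the foundation for a larger phase III study.

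**Working it through.** **1. The plan's own figure.** Section 11.3 inputs: medians 4.2 and 6.0 months, 24 months' uniform accrual, 9 months' follow-up, exponential deaths, one-sided 0.10, 40 patients. With λ = ln2/6.0:

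- P(death) = 1 − [exp(−9λ) − exp(−33λ)]/(24λ) = 0.880, or 35.2 deaths in 40.
- Power = Φ(ln(6.0/4.2)·√35.2 − 1.2816) = 79.8%.

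The stated 80% is reproduced. It rests on all 40 patients, so the subset does not touch it.

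**2. Minimum time to finish WBRT.** I read the 14 days in section 7.0 as treatment days, since 14 fractions at five a week do not fit into 14 calendar days. From first to last fraction is 17 days (Monday or Tuesday start) or 19 days (Wednesday to Friday start). Adding the 6-day minimum lead-in gives 23 or 25 days from the first dose. A longer lead-in or missed sessions would lengthen this.

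**3. Effect of excluding early deaths only.** Assume no treatment effect (true median 4.2) and exponential survival. Let L = days/30.44 and λ0 = ln2/4.2. The share excluded is 1 − exp(−λ0·L), and the apparent median is 4.2 + L.

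| Survival counted from | Days | Excluded | Apparent median (months) |
|---|---|---|---|
| First dose | 23 | 11.7% (4.7 of 40) | 4.96 |
| First dose | 25 | 12.7% (5.1 of 40) | 5.02 |
| First fraction | 17 | 8.8% | 4.76 |
| First fraction | 19 | 9.8% | 4.82 |
| End of WBRT | – | – | 4.20 (no shift) |

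**4. Dependence on the shape of survival.** Assume Weibull survival with median 4.2, shape k and 25 days from the first dose, so L/4.2 = 0.1955. The apparent median is 4.2·[1 + 0.1955^k]^(1/k), and the share excluded is 1 − exp(−ln2·0.1955^k).

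| Shape k | Excluded | Apparent median | Shift |
|---|---|---|---|
| 0.8 | 17.1% | 5.67 | +1.47 |
| 1 (exponential) | 12.7% | 5.02 | +0.82 |
| 1.25 | 8.6% | 4.63 | +0.43 |
| 1.5 | 5.8% | 4.44 | +0.24 |

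Against the planned gain of 6.0 − 4.2 = 1.8 months, the range is 0.24/1.8 = 13% to 1.47/1.8 = 82%.

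**5. If patients still on drug at the data cut are also left out.** This removes some long survivors and pulls the other way. The documents give no progression times, so I assume medians of 2 to 4 months, count death on drug as completed, and simulate Kaplan-Meier medians counted from the first dose.

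- Progression independent of death: 4.92-5.02 months with 9 months' follow-up; 4.59-4.87 if analysed when accrual ends.
- Progression correlated 0.8 with death (Gaussian copula), progression median 4 months: about 4.8 with 9 months' follow-up; about 4.2 at the end of accrual, which is essentially no shift.

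**6. What a landmark at the end of WBRT leaves behind.** Counting from the landmark removes the guaranteed time. Suppose, however, that a fraction f of those who would die within t months after it have stopped WBRT and are excluded. The median is then 4.2·[1 − log2(1 − f·F)], with F = 1 − exp(−λ0·t). For f = 25%, t = 1 it is 4.43; for f = 50%, t = 1 it is 4.68; for f = 50%, t = 2 it is 5.12. These fractions are assumptions; the documents give no stopping rates.

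**The case against.** Intent-to-treat governs, and the subset is one added sentence with no test, comparator or decision rule. Reporting treatment completers beside all patients is common. The size is not pinned down: with a low early hazard, which is plausible but not established for patients entering with KPS of at least 70, the shift is small. On one reading of the Tarceva condition even the direction is in doubt.

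Most of this stands, and it limits the point. Three stronger readings might be inferred, and the documents support none of them.

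- *That the trial's primary result or error rate is biased.* Section 11.3 is sized on all 40 patients, and its test is not assigned to the subset. A false-positive rate for the subset would describe an analysis that the plan does not propose.
- *That the shift is known to be close to 0.8 month.* That figure needs a constant hazard and time counted from the first dose. The documents give no time origin, and section 11.3 assumes exponential survival only for the sample size.
- *That controls will be picked with their survival in view.* Section 11.5.1.1 says only that all cases are reviewed when several RTOG 0118 patients match. This permits such a choice but does not show it, and the bias could go either way.

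What the objection does not remove: the definition cannot be applied as written, and on every reading membership depends on events after enrolment.

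**Conclusion.** The point holds for the evaluable subset only. Its definition conditions on post-enrolment events and uses a completion criterion that has no meaning for an open-ended drug. Counted from the first dose, the subset's survival is likely to be biased upward. The central illustration is 4.2 becoming about 5.0 months, with 12-13% of patients excluded. It assumes no treatment effect, exponential survival and exclusion of early deaths alone. Other assumptions give about +0.2 to +1.5 months (Weibull shapes 1.5 to 0.8), no shift from deaths alone if time starts at the end of WBRT, or almost none if patients still on drug at an early data cut are dropped and progression is strongly correlated with death. The intent-to-treat Kaplan-Meier median, the comparison with 4.2 months in section 11.3 and the sample size of 40 all stand. The plan should be changed, but its main conclusion is not at risk.

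**What to change.** In section 11.2:

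1. Remove completion of Tarceva from the definition of evaluable.
2. Analyse patients who completed WBRT from a landmark at the end of WBRT, and count survival from that point.
3. Label the result supportive to intent-to-treat, and state that it is not to be set against a 4.2-month median counted from the start of treatment.
4. Report how many patients did not complete WBRT, and why.

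**Cost.** Plan wording and a little programming; N and power do not change. The result describes only patients who reach the landmark, 87-88% of them if only early deaths are lost under the exponential assumption. The landmark does not remove selection of patients who stop WBRT because they deteriorate (step 6 of the working), so the plan should state that limit.

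**Minor note, separate from the main point.** Before control survival is examined, section 11.5.1.1 should state which RTOG 0118 arm supplies the matched controls and how one is chosen when several match.

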11.3 Sample Size

We assume that the true median survival for the historical control is 4.2 months (averaging to the historical value for class 2), and we assume that the true median survival will be increased by 43% to 6.0 months with this therapeutic approach. This represents a hazard ratio (experimental/historical) of 0.70. We assume uniform accrual over 24 months, an additional follow-up period of 9 months, exponentially distributed death times. The exponential MLE test for a single arm study at the one-sided 0.10 significance level will yield 80% power to detect an increase in median survival from 4.2 to 6 months with a sample size of 40 patients.

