4.0 Eligibility Criteria

4.1 Inclusion Criteria

- 4.1.1 Histological confirmation of non-small cell lung cancer
- 4.1.2 Patients who have been treated in the past with Stereotatic radiosurgery, Stereotactic Radiotherapy, GliaSite or surgical resection will be allowed to enroll in this study
- 4.1.3 A diagnostic contrast-enhanced MRI or CT scan must be performed, demonstrating brain metastases
- 4.1.4 Age 18-70
- 4.1.5 Patients must have KPS \geq 70
- 4.1.6 Patients cannot be treated on any other treatment related clinical protocols within 30 days prior to study entry or during participation in the study
- 4.1.7 No uncontrolled or symptomatic major medical illnesses or psychiatric impairments, such as Alzheimer's or schizophrenia
- 4.1.8 Screening Clinical Laboratory Values: ANC >1500/ul, Platelets >80,000/ul, baseline AST and/or ALT within normal limits (within 30 days of starting protocol treatment).
- 4.1.9 All women of childbearing potential (A woman of child-bearing potential is a sexually mature woman who has not undergone a hysterectomy or who has not been naturally postmenopausal for at least 24 consecutive months [i.e., who has had menses at any time in the preceding 24 consecutive months]) and male participants must practice effective contraception (abstinence, oral, injectable, or implantable hormonal contraceptive; tubal ligation; intra-uterine device; barrier contraceptive with spermicide; or vasectomized partner) throughout the study. All women of child-bearing potential must have a negative serum pregnancy test and practice birth control while on study.
- 4.1.10 Patients must provide verbal and written informed consent to participate in the study

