11.0 Statistical Consideration

Phase II study of 20 patients (40 in total when combined with the Arizona study) to determine the effect of combining whole brain radiation with Tarceva. From what has been observed from the initial 15 patients enrolled at the Arizona Cancer Center, we would expect the vast majority of patients, to be in recursive partitioning analysis (RPA) class II, with the remaining falling into class I and a small percentage in class III. From the first 15 patients enrolled 4 remain alive, of the patients that passed away the median survival has been 9.5 months, while the RPA predicted survival was 4.2 months. While the initial result from the Arizona study are encouraging accrual has been longer than expected, which is why we have proposed to open a similar study here at MD Anderson. If this initial phase II study is successful it will serve as the foundation for a much larger multi-institutional phase III study.

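### The single 4.2-month null in section 11.3 ties the false-positive rate to an unstated RPA class mix; class-specific null hazards remove this modest distortion at almost no cost

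*Combined protocol and SAP*

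**What the plan says.** - **Null and test.** Section 11.3: "We assume that the true median survival for the historical control is 4.2 months (averaging to the historical value for class 2", with a gain to 6.0 months (hazard ratio 0.70). "The exponential MLE test for a single arm study at the one-sided 0.10 significance level will yield 80% power" with 40 patients, 24 months of uniform accrual, 9 further months of follow-up and exponential death times.
- **Class figures.** Section 11.2 gives 4.2 months for Class 2, and for the other two: "Class 1 patients with KPS >70 and age <65yrs to live approximately 7.1 months" and "Class 3 patients with KPS < 70 have an average survival of 2.3 months".
- **Expected mix.** Section 11.0: "we would expect the vast majority of patients, to be in recursive partitioning analysis (RPA) class II". It places the others in Class I, apart from a few in Class III. For the 15 Arizona patients already enrolled, section 11.2 reports that "the vast majority fall into RPA class II, with the reaming falling into class I and a small percentage in class III". Neither section gives counts or shares.
- **Eligibility.** Criterion 4.1.5 begins "Patients must have KPS" and sets a floor of 70, which excludes Class 3 as 11.2 defines it.
- **Class definition.** The lead-in to the class list in 11.2 names age, KPS and control of primary disease. Section 3.0 names age, performance status and extracranial metastasis.
- **Other analyses.** Section 3.0 plans a database comparison stratified by RPA class. Section 11.5.1.1 plans Kaplan-Meier estimates with a 95% interval, survival by class, and matching to RTOG 0118. It does not name the exponential MLE test.

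**The concern.** A fixed null of 4.2 months is the right benchmark for a Class 2 population. If some patients carry a 7.1-month expectation and too few carry a 2.3-month expectation to offset them, the pooled group will tend to outlive 4.2 months with no drug effect. The test then rejects more often than its stated 10%, always in the drug's favour. The plan says that success would be the foundation for a multi-institutional phase III trial, so part of an apparent gain could be case mix. Only the 11.3 test has a stated alpha and power, and neither is tied to a stated mix.

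**Working it through.** **1. The plan's own power.** With hazard λ = ln2/median, accrual A = 24 and follow-up F = 9, the death probability is 1 − [exp(−λF) − exp(−λ(A+F))]/(λA).

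- Median 4.2: 0.944, or 37.8 deaths of 40.
- Median 6.0: 0.880, or 35.2 deaths of 40.
- Log-scale power = Φ(ln(6/4.2)·√35.2 − 1.2816) = Φ(0.357 × 5.93 − 1.2816) = 0.798.

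The stated 80% reproduces. Simulation with all patients in Class 2 gives 0.791 (log form) and 0.817 (exact gamma form).

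**2. False-positive rate by mix.** Inputs are the three class figures in 11.2, read as medians as 11.3 does, with exponential survival within class and no treatment effect. Each mix has 200,000 simulated trials with fixed class counts. D is deaths and T is total follow-up time.

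- Log form: reject if √D·ln(T·(ln2/4.2)/D) > 1.2816.
- Gamma form: reject if 2T·ln2/4.2 exceeds the 0.90 quantile of chi-square on 2D degrees of freedom.

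The mixes are assumptions, because the plan gives no shares. The mix median solves Σ wₖ·exp(−ln2·x/mₖ) = 0.5, where wₖ is the share of class k and mₖ its median.

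| Class 1/2/3 of 40 | Mix median (months) | Rejection, log form |
|---|---|---|
| 0/40/0 | 4.20 | 8.6% |
| 2/36/2 | 4.17 | 9.3% |
| 3/34/3 | 4.15 | 9.8% |
| 3/35/2 | not computed | 11.1% |
| 4/34/2 | 4.27 | 13.1% |
| 5/32/3 | 4.25 | 13.5% |
| 4/35/1 | 4.34 | 14.6% |
| 5/33/2 | 4.32 | 15.3% |

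The first row is the reference. The other seven fit the descriptions in 11.0 and 11.2 and span about 9-15%. In the gamma form the reference is 10.2% and the same seven mixes span about 11-18% (5/33/2: 17.7%). The upper end is not a hard bound: 6/32/2, one step outside these mixes, gives 17.6% in the log form.

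Rejection can rise while the mix median hardly moves, because the exponential MLE uses total time per death and long Class 1 survivors weigh on it. At 2/36/2 the mix median is 4.17 months, but the MLE-based median averages 4.25.

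**3. Class-specific null.** Let E = Σ (patient's follow-up time × ln2/m), with m = 7.1, 4.2 or 2.3 by class. Reject if (E − D)/√E > 1.2816. Over 22 mixes the type I error is 8.5-8.7% and the power at hazard ratio 0.70 is 78.3-79.2%. The gamma form with E gives 10.2-10.4% and 80.9-81.7%.

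**The case against.** **The averaging assumption is declared and nearly holds.** On the fitting mixes the null median is off by at most 4.34 − 4.20 = 0.14 months, against a targeted gain of 6.0 − 4.2 = 1.8. This stands, and it is why the effect is modest.

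**The plan leans on estimation and already looks at case mix.** Section 11.2 calls the objective estimation of the median, and the class-stratified estimates, matching and database comparison address case mix. This stands in part. Those analyses do not change the null of the one test that sizes the trial, and section 2.1 frames the primary aim as improvement over historical controls.

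**Two stronger readings are tempting, and the documents do not support them.**

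- A reader might infer from criterion 4.1.5 that there are no Class 3 patients, and quote 4/36/0 (about 16% log form, 19% gamma form) or 8/32/0 (about 27% log form). But 11.2 reports Class III patients in the Arizona cohort, which is to be pooled and analysed by intent-to-treat. Those rows apply only if that report is wrong.
- A reader might infer a sharp rule: the level holds only if Class 1 is almost absent or matched by Class 3. That boundary belongs to the log form, which starts at 8.6%. In the gamma form 1/39/0 gives about 12% and 4/32/4 gives 12.1%. Even in the log form, matching drifts to 11.9% at 8/24/8.

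**The Class 1 line in 11.2 omits the third factor.** Taken alone it would put most eligible patients in Class 1. It is better read as shorthand, because the lead-in names control of primary disease. What stands is that 11.2 and 3.0 differ on that factor.

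**Conclusion.** The concern holds as a modest weakness in the choice of null. The false-positive rate of the 11.3 test is not fixed by the plan. It depends on an unstated class mix and rises when Class 1 outnumbers Class 3. On assumed mixes that fit 11.0 and 11.2, it runs from about 1 point below nominal to about 5 above in the log form, and from about 1 to 8 points above in the gamma form.

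This rests on the class figures being medians, on exponential survival within class, and on reading the plan's wording as 2 to 5 Class 1 and 1 to 3 Class 3 patients of 40. The sample-size arithmetic is sound. The change is worth making because it is cheap and uses figures already in 11.2.

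**What to change.** 1. In 11.3 and 11.5.1.1, name one primary test: the one-sample log-rank (E − D)/√E, rejecting above 1.2816 (one-sided 0.10). E sums each patient's follow-up time multiplied by ln2/7.1, ln2/4.2 or ln2/2.3 according to baseline RPA class.
2. Keep N = 40 and hazard ratio 0.70. State power as about 79%, or about 81-82% if the exact gamma form with E is used.
3. State the expected class mix in 11.3.
4. Use one RPA class definition throughout, settling the third factor on which 11.2 and 3.0 differ, and record class at baseline.
5. Reconcile the Class III statements in 11.0 and 11.2 with the KPS criterion in 4.1.5.

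**Cost.** Short edits to 3.0, 11.0, 11.2, 11.3 and 11.5.1.1, and about 1 point of power or less. The planned class strata already require the data.

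**Downside.** The test depends on correct class labels. At 5/33/2, labelling one or two Class 1 patients as Class 2 gives about 10% or 12% type I error, still below the 15.3% of the single null. The reverse error costs power: at 4/36/0, labelling one or two Class 2 patients as Class 1 gives 76.8% or 75.1%.

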11.5.1 Endpoint Analysis

11.5.1.1 Survival

We will use the product limit estimator of Kaplan and Meier (1958) to estimate the overall survival of all patients using the intent-to-treat principle. We will report the median survival and its associated 95% confidence interval.

We will also estimate overall survival stratified by treating institution and class, as described above in section 11.2.

We will compare the estimates of survival from this study with a recent reported phase III randomized RTOG trial, 0118, which randomized 332 patients to WBRT with or without Thalidomide (19). Our patients will be compared to both the overall survival and CNS progression free survival from this study.

We will tabulate cause of death by treating institution and by class, and we will compare the cause of death for patients in this study with patients from RTOG 01188.

We will analyze progression-free survival (PFS) in the same manner as overall survival.

We will use the methods described in Klein and Moeschberger (1997) to test for differences in survival between the matched pairs. To help us understand how similar/dissimilar patients from MDACC and Arizona are we will summarize the demographic and clinical characteristics of these patients separately. We will also estimate the survival of the 40 patients (20 from MDACC and 20 from AZCC) with the product-limit estimator of Kaplan and Meier (1958) stratified by study center (MDACC, AZCC), and we will use Cox (1972) proportional hazards regression to model survival of these 40 patients as a function of study center and estimate the hazard ratio (MDACC:AZCC) with a 95% confidence interval. For the match control based variables we will use patients from a prior randomized whole brain radiation therapy (WBRT) study performed by the Radiation Therapy Oncology Group (RTOG) study (RTOG 0118). Patients will be matched based on age, KPS, number of brain metastasis and control of systemic disease. If there is more than one match available for a patient we will review all cases.

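### The 4.2-month null and the unmatched RTOG 0118 comparison carry no age restriction, while the trial stops at age 70; the benchmarks may be too low for the patients enrolled, by an amount the documents cannot settle

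*Combined protocol and SAP*

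**What the plan says.** Section 2.1 makes improvement in median survival over historical controls the primary aim; there is no concurrent control arm. Section 11.3 fixes the control value: "We assume that the true median survival for the historical control is 4.2 months (averaging to the historical value for class 2". It then states that "we assume that the true median survival will be increased by 43% to 6.0 months with this therapeutic approach" and that the test "will yield 80% power to detect an increase in median survival from 4.2 to 6 months with a sample size of 40 patients", at a one-sided level of 0.10.

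The 4.2 months comes from section 11.2, which attributes it to 1200 patients in three earlier RTOG trials: "Class 2 patients not meeting Class 1 or 3 criteria, have an average survival of 4.2 months". In the same list Class 1 requires age under 65 and Class 3 requires KPS below 70. Class 2 is what remains, and no upper age is written for it. Neither the age limits nor the age distribution of the 1200 patients is given.

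Section 4.1 limits entry to ages 18 to 70 (4.1.4) and KPS of at least 70 (4.1.5). Section 3.0 calls the Arizona study identical, so on the plan's own account the pooled 40 patients share these limits.

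Section 11.5.1.1 adds a comparison with the 332-patient RTOG 0118 trial: "Our patients will be compared to both the overall survival and CNS progression free survival from this study". No restriction of those controls by age or KPS is stated. The same section separately plans matched controls from RTOG 0118, with age and KPS among the matching variables.

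**The concern.** Under the definitions in section 11.2, a historical patient over 70 with KPS of 70 or more cannot be Class 1 (too old) or Class 3 (KPS too high). Any such patient falls in Class 2 and contributes to the 4.2 months. Section 4.1.4 keeps the same kind of patient out of this trial.

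The plan treats age as prognostic: section 3.0 names it as an RPA factor and section 11.5.1.1 matches on it. If older Class 2 patients in the source trials died sooner, Class 2 patients aged 70 or under would be expected to live longer than 4.2 months without Tarceva. A single-arm comparison would then credit part of the entry criterion to the drug. The unmatched RTOG 0118 comparison is open to the same problem, and also to a KPS mismatch if that trial enrolled patients below 70.

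This differs from having the wrong mix of RPA classes, because it would remain if every enrolled patient were Class 2. Section 11.0 says that success here would be the foundation for a phase III study, so an optimistic benchmark has consequences.

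**Working it through.** **Inputs from section 11.3.** Null median 4.2 months; alternative 6.0 months; N = 40; accrual A = 24 months; follow-up F = 9 months; exponential survival; one-sided 0.10, so z = 1.2816.

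**Step 1: reproduce the plan's power.** With λ = ln 2 / m, the expected number of deaths at true median m is

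d(m) = 40 × {1 − [exp(−λF) − exp(−λ(A+F))] / (λA)}.

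This gives d(6.0) = 35.2 and d(4.2) = 37.8. On the log scale, the probability of rejecting null m0 is

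Φ( ln(m/m0) × √d(m) − 1.2816 ).

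For 6.0 against 4.2: ln(6.0/4.2) = 0.3567 and √35.2 = 5.93, so Φ(2.117 − 1.2816) = Φ(0.835) = 79.8%. The stated 80% reproduces, as does the hazard ratio (4.2/6.0 = 0.70). The arithmetic of section 11.3 is sound.

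**Step 2: sensitivity to the null.** Suppose Tarceva has no effect and the true median of eligible patients is m, but the test is still against 4.2:

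| True untreated median (months) | Rejection rate |
|---|---|
| 4.2 | 10.0% |
| 4.3 | 12.8% |
| 4.37 | 15% |
| 4.5 | 19.5% |
| 4.6 | 23.4% |
| 5.0 | 41.1% |

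At 4.37, for example: ln(4.37/4.2) = 0.0397, √37.5 = 6.13, and Φ(0.243 − 1.2816) = 15%. The shift of 0.17 month is about 5 days. Simulating the same test gave slightly lower rates (8.6% at 4.2, 14.2% at 4.4, 21.7% at 4.6) and 79.1% power at 6.0, so the pattern does not depend on the approximation.

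**Step 3: what an over-70 subgroup would do.** The documents give no inputs here; the share s and the over-70 median mo are assumptions. If Class 2 as a whole has median 4.2, the median my of those aged 70 or under solves

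s × 0.5^(4.2/mo) + (1 − s) × 0.5^(4.2/my) = 0.5.

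For s = 10% and mo = 3.0: 0.5^1.4 = 0.379; (0.5 − 0.0379)/0.9 = 0.5135; my = 4.2 × 0.6931/0.6666 = 4.37. Each cell shows my in months and the resulting false-positive rate against 4.2:

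| Over-70 share | mo = 3.5 | mo = 3.0 | mo = 2.3 |
|---|---|---|---|
| 0% | 4.20; 10% | 4.20; 10% | 4.20; 10% |
| 5% | 4.24; 11% | 4.28; 12% | 4.34; 14% |
| 10% | 4.29; 12% | 4.37; 15% | 4.51; 20% |
| 15% | 4.34; 14% | 4.47; 18% | 4.70; 28% |
| 20% | 4.40; 16% | 4.59; 23% | 4.94; 38% |

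The 2.3-month column borrows the plan's Class 3 value and is a pessimistic bound, because these patients would be Class 2.

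**Step 4: cost of moving the null.** With N = 40 and 6.0 months as the alternative, power is 73% against 4.37, 68% against 4.47 and 62% against 4.59.

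**Step 5: cost of an estimated null.** If a control median estimated from D deaths were treated as fixed, the true one-sided error would be Φ(−1.2816/√(1 + 37.8/D)). That is 17% for D = 50 and 14% for D = 100 (D is assumed).

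**The case against.** A reader might infer that the historical benchmark does contain patients over 70 and is therefore too low. The documents do not support that. A class definition without an upper age describes how patients are sorted; it does not show who was enrolled in the three source trials, or in RTOG 0118. Nor is any survival difference given within Class 2 above and below 70; the only printed age cut is 65. The direction is plausible because the plan treats age as prognostic, but the size is unknown and could be close to nil. This part of the objection stands, and the point is therefore conditional.

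It can also be said that the plan already handles age by matching on it, that survival is to be reported by class, and that the exponential test appears only in the sizing section, while the analysis section plans Kaplan-Meier estimates with a 95% interval. This is correct as far as it goes. However, the matched analysis is separate, and it leaves both the 4.2-month reference and the unmatched RTOG 0118 comparison without an age restriction. Reporting by class does not remove an age difference within Class 2.

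A better documented reason why 4.2 months may be low is that Class 1 patients, at 7.1 months, are eligible and expected (section 11.0). A 10% or 20% Class 1 share alone would lift the untreated median to 4.41 or 4.63 months. That is a different question, and it adds to this one.

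Finally, replacing 4.2 with a median estimated from filtered controls would not be a clean remedy. It would bring in sampling error (step 5), mix in Class 1 controls unless the filter is by class, and lower power appreciably (step 4). This also stands, and it shapes the fix.

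**Conclusion.** The concern holds as a conditional risk. It is documented that the null is a whole-Class-2 value, that Class 2 as printed has no upper age, that entry stops at 70, and that neither the null nor the unmatched RTOG 0118 comparison is limited to age-eligible patients. It is not documented that the benchmarks are in fact too low. Under assumed over-70 shares of 5% to 20% and medians of 2.3 to 3.5 months, the nominal 10% one-sided error would be about 11% to 38%; with no patients over 70 it stays at 10%. These figures also assume exponential survival and the accrual and follow-up stated in section 11.3. The sample-size calculation itself is correct for the null it names.

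**What to change.** 1. **Section 11.5.1.1.** Restrict the unmatched RTOG 0118 comparison, for both overall survival and CNS progression-free survival, to control patients who meet this protocol's measurable entry criteria: at least age 18 to 70 and KPS of 70 or more. The planned matching already needs patient-level data. Report the comparison by RPA class, so that class mix is not confounded with the age restriction.
2. **Section 11.3.** Keep 4.2 months as the fixed sizing null, but state that it is a whole-Class-2 value with no age restriction.
3. **Sensitivity analysis.** Compare with age-eligible Class 2 controls, using a method that allows for the sampling error of the control estimate and does not treat it as a known constant.

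The cost is some SAP wording, one filter on control data the plan already uses, fewer control patients and less precision. If the sponsor chose to adopt a higher null instead, power at 6.0 months with 40 patients would fall from 80% to about 73% at a null of 4.37 and 62% at 4.59, and that loss would have to be disclosed.
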